3.7. OTHER EFFECTIVENESS ENDPOINTS

Other effectiveness endpoints include:

- Average hours of use per day
- Change in HbA1c levels at each 6-month interval from baseline

3.8. PATIENT PERSPECTIVE ENDPOINT

Patient experiences with the CGM system will be assessed using the CGM Satisfaction Survey which is a validated patient satisfaction questionnaire specifically developed for CGM systems by the Juvenile Diabetes Research Foundation (JDRF) Continuous Glucose Monitoring Study Group. Patients will complete the CGM Satisfaction Survey (a 44-item questionnaire) at 6 months and at 12 and 24 months.

Patients will also complete the Diabetes Distress Scale, which is a 17-item scale that measures four dimensions of distress (emotional burden, regimen distress, interpersonal distress, and physician distress). Patients will complete the Diabetes Distress Scale at baseline, 6, 12 and 24 months.

3.9. HCP PERSPECTIVE ENDPOINT

3.10. OTHER ENDPOINTS

Other study endpoints include:

- Success rate of insertion and removal procedures, overall and by HCP experience to evaluate training program.
- Rate of serious adverse events based on HCP experience with the insertion and removal of Sensors (learning curve by number of cases)

4. STUDY POPULATION

The PAS will enroll up to 400 subjects (to insert 273 subjects) to ensure adequate numbers of subjects for the primary safety endpoint.

Senseonics, Inc. Confidential Information Protocol #: CTP-0034, Version 10

Page 17 of 43

Effective Date:#: 20 March

4.1. INCLUSION CRITERIA

Subjects may be included in the PAS if they fit the following inclusion criteria:

- 1. Subject has diabetes
- 2. Subject is greater than 18 years of age

4.2. EXCLUSION CRITERIA

Subjects may not be included in the PAS if they fulfill the following exclusion criteria:

- 1. Subject is critically ill or hospitalized
- 2. Subject has a known contraindication to dexamethasone or dexamethasone acetate
- 3. Subjects requiring intravenous mannitol or mannitol irrigation solutions
- 4. Female subjects who are pregnant, planning on becoming pregnant or nursing
- 5. Subjects on hybrid closed loop systems or closed loop systems
- 6. Subjects on other CGM systems

4.3. CRITERIA FOR SUBJECT WITHDRAWAL OR DISCONTINUATION

A subject may choose to withdraw at any time for any reason without adverse effect on their care. The subject will continue with their medical follow-up, according to standard-of- care.

The treating HCP may also choose to withdraw a subject from the study, if in the best medical interest of the subject or compliance with study requirements cannot be maintained.

5. STUDY DESIGN

5.1. OVERVIEW

This is a prospective, multi-center study, whereby up to 400 subjects will be enrolled in the United States at up to 30 sites to achieve at least 1400 Sensor wear cycles at the end of the study. The subjects will have one Sensor inserted by trained HCP (physicians, physician assistants, and/or nurse practitioners) approximately every 3 months (for the 90-day Eversense Sensor) or 6 months (for the 180-day Eversense E3 Sensor). Sensors will be inserted in the upper arm of the subjects.

Follow up visits are anticipated at approximately 3- or 6- month intervals. A Sensor removal and reinsertion will be arranged once the current Sensor reaches its end of life. At each Sensor insertion and/or removal the treating HCP will be asked to report on the ease of the procedure and on any complications that occurred.

Senseonics, Inc.
Protocol #: CTP-0034, Version 10

Confidential Information

Page 18 of 43

2023

Effective Date:#: 20 March

5.1.1. VISIT SCHEDULE

Visit 1 Enrollment/Sensor insertion Visit. Following the informed consent process, the screening evaluation will determine subject eligibility for Sensor insertion. Screening will include medical and diabetes history, physical examination, laboratory assessments and questionnaires. Sensors are inserted by a health care professional in the upper arm. Subject training on study and devices. Visit lasting approximately 2 to 3 hours.

5.1.1.1. SCHEDULE FOR SUBJECTS WHO ONLY RECEIVE EITHER 90-DAY OR 180-DAY **SENSORS:**

- 90-day Sensor Visits 2-8 Follow-up/Sensor replacement Visit (Days 90, 180, 270, 360, 450, 540, and 630) after Visit 1 (90 days ±7 days after each insertion).
- 180-day Sensor Visits 2-4 Follow-up/Sensor replacement Visit (Days 180, 360, 540) after Visit 1 (180 days ±7 days after each insertion)

A safety evaluation will be performed including examination of Sensor sites and collection of adverse events. Sensor replacements will occur at these visits, laboratory assessments every 6 months and questionnaires as specified.

5.1.1.2. SCHEDULE FOR SUBJECTS WHO TRANSITION FROM 90-DAY TO 180-DAY **SENSORS:**

Visits for 90-day to 180-day Sensor transition subjects follow-up/Sensor replacement¹ range from Day 180 to Day 630 after Visit 1 (90- or 180-days ±7 days, dependent on prior Sensor).

Subjects will continue the 90-day visit schedule (section 5.3). A safety evaluation will be performed including examination of Sensor sites and collection of adverse events. Subjects will complete all required follow up testing and questionnaires. New Sensors will be inserted and removed at appropriate intervals.

5.2. FINAL FOLLOW-UP/SENSOR REMOVAL VISIT:

5.2.1. SCHEDULE FOR SUBJECTS WHO ONLY RECEIVE A 90-DAY OR 180-DAY SENSOR:

• 90-day Sensor – Day 720 after Visit 1 (90 days ±7 days after final insertion (Visit 9)

Page 19 of 43

Senseonics, Inc. Confidential Information Effective Date:#: 20 March Protocol #: CTP-0034, Version 10

¹ Some subjects will have a hybrid of 90-day and 180-day Sensors due to starting the study with 90-day Sensors

 180-day Sensor – Day 720 after Visit 1 (180 days ±7 days after final insertion for 180day Sensor [Visit 5]

A safety evaluation will be performed including examination of Sensor sites and collection of adverse events. Sensor removal, laboratory assessment and questionnaires will occur at this visit.

5.2.2. SCHEDULE FOR SUBJECTS WHO TRANSITION FROM 90-DAY TO 180-DAY SENSORS:

Subjects who transition to the 180-day Sensor at 90-, 270-, 450- or 630-day visit will have a safety evaluation performed at the 720-day visit ±7 days including examination of Sensor sites and collection of adverse events along with laboratory assessment and questionnaire administration. The Sensor will NOT be removed at this visit.

- Follow-up Assessment calls will be made 15 and 45 days after the 720-day visit.
- Ninety (90) days ±7 days or Sensor end-of-life (whichever is earlier) following 720-day visit
 in the above transition subjects, the subject will return to the clinic for Sensor removal
 followed by a phone call for AE assessment. This call designates final participation in the
 study.

Senseonics, Inc.

Confidential Information

Page 20 of 43

Protocol #: CTP-0034, Version 10

Effective Date:#: 20 March

5.4. VISIT DETAILS

5.4.1. VISIT 1 - ENROLLMENT/INSERTION

Subjects will be enrolled into the study following informed consent. Screening evaluation will determine subject eligibility for Sensor insertion. No study-specific procedures may be performed prior to informed consent signature.

The Enrollment/Insertion Visit includes performing/collecting the following information:

- Demographics- including age, gender at birth, race/ethnicity, and BMI.
- Diabetes History- including type of diabetes, date of diagnosis or length of diabetes, history of DKA and severe hypoglycemia, current treatment (type of insulin and type of insulin delivery (injections or insulin pump).
- Current and Past Medical History- including concomitant prescription medications.
- Physical examination and vital signs- including height, weight, blood pressure, pulse, temperature, assessment of potential Sensor insertion sites.
- Blood samples will be drawn for the following laboratory tests:
- Hemoglobin A1C
- Point of care testing
- Urine pregnancy test- for females of childbearing capacity (defined as not surgically sterile or not menopausal for ≥ 1 year)

5.4.1.1. SENSOR INSERTIONS

A trained study HCP (physicians, physician assistants, and/or nurse practitioners) will insert the Sensor into the subcutaneous tissue using appropriate technique described in the Eversense CGM Sensor Insertion and Removal Instructions. The location of each Sensor will be documented.

Subjects will be advised that they may take over the counter pain medication if needed for any discomfort after the insertion process. No medication, including medication-containing creams and patches is to be applied over the Sensor insertion site.

Subjects will be advised to keep the area dry for 24-48 hours. Subjects will be advised to change the dressing approximately 48 hours post insertion, and they will check that the healing process is going as expected (minor redness, no swellings, no increased temperature, no increased pain and no sign of infection). The subjects will be instructed to leave the steri-strips in place until they fall off on their own. If the edges of the strips s, Inc.

Confidential Information

Page 23 of 43

Senseonics, Inc. Confidential Information Page 23 of 43
Protocol #: CTP-0034, Version 10 Effective Date:#: 20 March

peel back, they may be trimmed. After 48 hours subjects will be advised to change the dressing as required until the incision is healed. Cleaning can be done with normal saline in the clinic, but at home they can use tap water.

Identification of the Sensor, transmitter and accessories will be recorded (part number, serial number, lot number, and expiration date as applicable).

After Sensor insertion, the transmitter will be worn briefly (approximately 20 minutes) to ensure proper operation of the system (confirmation of system operation).

5.4.1.2. DEVICE DISBURSEMENT

Subjects will be assigned the following devices:

- o Eversense Continuous Glucose Monitoring (CGM) Systems consisting of:
- One Transmitter (for Eversense or Eversense E3 CGM System as appropriate) and accessories (charger, adhesive patches)
- Eversense or Eversense E3 CGM System User Guides, as appropriate

The clinical site staff will assist the subject with loading the appropriate Eversense Mobile Medical App (MMA) on their handheld device (smartphone or iPod Touch) as needed.

5.4.1.3. SUBJECT TRAINING

The subject will be provided both verbal and written instructions for proper incision care of the insertion site. The subject will be given instructions on how to contact study staff for 24 hours per day to report any study- related problems. The subject will be instructed to contact the study staff for prolonged hyperglycemia, severe hypoglycemia, or if he/she experiences nausea, vomiting, or abdominal pain within 48 hours after discharge. The subject will be instructed to contact the study staff for any problems related to the Sensor sites, including fever, pain, redness, itching, discharge, warmth or swelling at the Sensor insertion sites. If infection is experienced, standard medical practice and administration of antibiotics as required should be followed until resolution.

The subject will be instructed on the proper use of the Transmitter and Mobile Medical Application (refer to the Eversense and Eversense E3 CGM User Guides). The transmitter should be worn over the Sensor starting approximately 24 hours post insertion. Subjects will be prompted to calibrate the Sensor using fingerstick measurements (a minimum of 2 each day, approximately 12 hours apart for the Eversense CGM System or 2 each day for the first 20 days transitioning to primarily 1 per day on day 21 for the Eversense E3 CGM System) using their BG meter.

Senseonics, Inc. Confidential Information Page 24 of 43
Protocol #: CTP-0034, Version 10 Effective Date:#: 20 March

5.4.1.4. QUESTIONNAIRES

Subjects will be asked to fill out a short questionnaire (DDS) about their diabetes.

HCPs will fill out a short questionnaire regarding their experience with the insertion/removal procedure device use and training on a periodic basis

5.4.1.5. DISCHARGE

Discharge will occur upon completion of confirmation of system operation and subject training. The site will document any adverse events that may have occurred during the visit.

5.4.1.6. ESTIMATED VISIT DURATION

Study visit is approximately 2-3 hours.

5.4.2. FOLLOW-UP/SENSOR REPLACEMENT VISITS

90 Day Sensor

- Visit 2 Day 90 (90 days ±7 days after first insertion)
- Visit 3 Day 180 (90 days ±7 days after second insertion)
- Visit 4 Day 270 (90 days ±7 days after third insertion)
- Visit 5 Day 360 (90 days ±7 days after fourth insertion)
- Visit 6 Day 450 (90 days ±7 days after fifth insertion)
- Visit 7 Day 540 (90 days ±7 days after sixth insertion)
- Visit 8 Day 630 (90 days ±7 days after seventh insertion)

180 Day Sensor

- Visit 2 Day 180 (180 days ±7 days after first insertion)
- Visit 3 –Day 360 (180 days ±7 days after second insertion)
- Visit 4 Day 540 (180 days ±7 days after third insertion)

The above visit days and windows are approximate. Sensor life is either 90 or 180 days and will stop providing glucose values after 90 or 180 days. In the event that a Sensor is replaced prior to or after the visit day listed above, the next Sensor replacement visit should be planned for 90 or 180 days (±7 days) depending on the Sensor inserted at the last Sensor insertion. If a Sensor stops functioning prior to the scheduled replacement visit, the visit may be rescheduled earlier.

Senseonics, Inc.
Protocol #: CTP-0034, Version 10

Confidential Information

Page 25 of 43

Effective Date:#: 20 March

The procedures/instructions listed below will be followed for Follow-up/Sensor Replacement Visits 2-8 (90-day Sensor) and Visits 2-4 (180-day Sensor) or as described above for Sensor transition subjects (Section 5.1.1.2).

5.4.2.1. SUBJECT ADMISSION

Female subjects of childbearing capacity will perform a urine pregnancy test. If positive, the subject will discontinue study participation. Subject withdrawal will be documented.

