6.1. ADVERSE EVENT DEFINITIONS

Adverse Event (AE) is defined as any untoward medical occurrence, unintended disease or injury, or untoward clinical signs (including abnormal laboratory findings) in subjects, users or other persons, whether or not related to the medical device.

- NOTE 1: This definition includes events related to the medical device or the comparator.
- NOTE 2: This definition includes events related to the procedures involved.

NOTE 3: For users or other persons, this definition is restricted to events related to medical devices.

Serious Adverse Event (SAE) is defined as an adverse event that:

- Leads to death;
- Leads to a serious deterioration in the health of the Subject that either:
 - o Results in life-threatening illness or injury; or
 - o Results in a permanent impairment of a body structure or a body function; or
 - o Requires inpatient or prolonged hospitalization; or
 - Results in medical or surgical intervention to prevent life-threatening illness or injury or permanent impairment to a body structure or a body function.
- Led to fetal distress, fetal death or congenital abnormality or birth defect

NOTE: Planned hospitalization for a pre-existing condition, or a procedure required by the CIP, without serious deterioration in health, is not considered a serious adverse event.

Anticipated adverse events are AEs that have been identified as possible adverse events related to the device or procedure.

Unanticipated adverse device effects (UADEs) are defined as any serious adverse effect on health or safety or any life-threatening problem or death caused by, or associated with, a device, if that effect, problem, or death was not previously identified in nature, severity, or degree of incidence in the study plan or application (including a supplementary plan or application), or any

Protocol #: CTP-0034, Version 10

Confidential Information

Page 29 of 43 Effective Date:#: 20 March

f: CTP-0034, version 10

2023

Senseonics, Inc.

other unanticipated serious problem associated with a device that relates to the rights, safety, or welfare of study subjects.

Severity

Mild: Awareness of a sign or symptom that does not interfere with the Subject's usual activity or is transient, resolves without treatment and with no sequelae

Moderate: Interferes with the Subject's usual activity and/or requires symptomatic treatment

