6.2.1. DATA SAFETY MONITORING BOARD

An independent data safety monitoring board will be established prior to the initiation of the study. Members will represent areas of expertise such as internal medicine and endocrinology and biostatistics. The DSMB will develop a charter and hold formal review meetings over the course of the study to assess the ongoing safety information collected as required by their charter. The DSMB will assess if the overall safety profile continues to be appropriate throughout the conduct of the study and immediately reassess if serious events such as death, serious deterioration of health or fetal distress are deemed related to the device.

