6.3.1. AE REPORTING PERIOD

Adverse events are reported from enrollment until study participation has ended. Adverse events will be followed until resolution, AE has stabilized, or the study has been completed.

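### A positive pregnancy test ends participation and adverse-event reporting with it, so fetal-outcome SAEs after detection are not captured

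*Protocol*

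**What the plan says.** Pregnancy is an entry exclusion (protocol Section 4.2: "Female subjects who are pregnant, planning on becoming pregnant or nursing"). Women of childbearing capacity are tested again at each replacement visit. Section 5.4.2.1 states the consequence of a positive result: "If positive, the subject will discontinue study participation". The only record it asks for is of the exit: "Subject withdrawal will be documented".

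Section 6.3.1 sets the reporting period: "Adverse events are reported from enrollment until study participation has ended". Its next sentence deals with events already on record: "Adverse events will be followed until resolution, AE has stabilized, or the study has been completed".

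Two other sections treat fetal outcomes as part of the safety data. The SAE definition in Section 6.1 includes an event that "Led to fetal distress, fetal death or congenital abnormality or birth defect". Section 6.2.1 has the DSMB "immediately reassess if serious events such as death, serious deterioration of health or fetal distress are deemed related to the device".

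The SAP (Sections 5.3, 5.4 and 5.8) summarises early exits by reason, tabulates AEs and SAEs, and imputes nothing. It does not mention pregnancy follow-up.

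**The concern.** The finding that makes a fetal-outcome SAE foreseeable is also the finding that stops its collection. The Sensor carries a ring that elutes dexamethasone (Section 1.1). Section 6.4 says it is not known whether the risks of injectable dexamethasone apply to the ring, and Section 6.6 plans an escalation for suspected steroid exposure. Because pregnant women are excluded at entry, inadvertent exposures will be few and each one informative.

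As the plan stands, a final report with no fetal-outcome SAEs after detection could not be told apart from a report in which nobody looked. The CEC and the DSMB can act only on events that reach them. A smaller part of the same gap concerns the Sensor still in place at the positive test: an infection or other procedure-related event that appears after the withdrawal visit belongs to the kind of event in the primary safety composite, yet falls after reporting has closed.

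**Working it through.** The plan states no figure on this point. The check sets the rules side by side and then does the window arithmetic.

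**Rules in sequence**

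1. Positive test: participation ends (5.4.2.1).
2. Participation ends: AE reporting ends (6.3.1, first sentence).
3. Together: an event with onset after the positive-test visit is outside the reporting period.
4. Exceptions sought:
   - Section 6.3.1, second sentence, follows AEs already recorded. The documents do not say whether a pregnancy is itself recorded as an AE, so this does not clearly carry a pregnancy to its outcome.
   - Section 4.3, on voluntary withdrawal, says "The subject will continue with their medical follow-up, according to" standard of care. That is routine care, not study data.
   - Section 5.3 times the routine calls from each insertion. A subject who gets no new Sensor triggers no new call. The call 30 days after removal is written only for subjects who moved from 90-day to 180-day Sensors.
   - The SAP contains none.

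**Longest time without a test, at nominal windows**

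| Situation | Source | Days |
|---|---|---|
| Between tests, 90-day Sensor | 5.4.2 | 90 + 7 = 97 |
| Between tests, 180-day Sensor | 5.4.2 | 180 + 7 = 187 |
| Last test to final call, transition subject | 5.3: last test Day 630; removal about Day 720 + 90 = 810; call 30 days later, Day 840 | 840 − 630 = 210; with the removal window, 210 + 7 = 217 |

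Assumption, not in the documents: conception to term delivery takes about 259 to 280 days. The longest window falls short by 259 − 217 = 42 to 280 − 217 = 63 days. The conclusion needs only that term takes longer than 217 days. If the Day 720 visit is also 7 days late, the window is 224 days and the conclusion is the same.

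So a pregnancy conceived after a negative test cannot reach a term outcome inside the reporting period. The windows are long enough for an earlier fetal loss or fetal distress to occur while the subject is still a participant, and those events are reportable.

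**Number of subjects.** The documents give neither the number of women of childbearing capacity nor a pregnancy rate. For scale only, assume 60 to 100 such women followed for 2 years at 1 to 3% per year: 60 × 2 × 0.01 = 1.2 to 100 × 2 × 0.03 = 6 pregnancies. Nothing below depends on this range.

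**The case against.** A reader might infer three stronger things, and the documents do not support them.

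- **That fetal SAEs can never be observed, or that the DSMB trigger cannot fire.** Section 5.4.2.2 documents AEs since the previous visit, provides calls at about 14 and 45 days after insertion, and reminds subjects to report events. A fetal event before a positive test, or in the untested time before exit, is inside the reporting period. An AE already open at withdrawal may be followed under the second sentence of 6.3.1, whose end point is completion of the study rather than of participation. Fetal distress is also only one of the DSMB examples, alongside death and serious deterioration.
- **That the Sensor removal itself goes unreported.** Testing is described before removal, but section order is not stated as procedural order: Section 5.4.2.4 describes the new insertion before the old removal. The subject is already at a removal visit, and events during that visit are to be documented. Only events after the visit are uncovered.
- **That pregnancy is ruled out as an AE.** The documents are silent. Section 6.3.3 lists what is not reported as an AE and does not name pregnancy.

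It is also fair to say that the CRFs, the DSMB and CEC charters and the consent form were not available and might provide for outcome follow-up, and that Section 6 defers to local requirements where they differ. None of this removes the conflict: the protocol sets two explicit rules whose combination closes reporting at detection, and an unseen document would have to contradict 6.3.1 to reopen it.

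**Conclusion.** The point holds for the period after detection. Followed as written, Sections 5.4.2.1 and 6.3.1 leave fetal-outcome SAEs with onset after a positive test uncollected, in conflict with the SAE definition in 6.1 and the DSMB role in 6.2.1. Term birth outcomes are the clearest loss; earlier fetal events are partly within reach. AEs that first appear after the withdrawal visit are not covered either.

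This rests on reading the end of participation in 5.4.2.1 and in 6.3.1 as the same moment, and, for term outcomes, on the assumed length of pregnancy. The number of subjects cannot be derived from the documents but is likely to be small. The 1,400-cycle sample size and the primary binomial test are unaffected. It is a gap in safety data that should be closed, not a threat to the primary conclusion.

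**What to change.** Reconcile Sections 5.4.2.1, 6.1, 6.2.1 and 6.3.1 on data collection. Amend 6.3.1 so that, for a subject discontinued for pregnancy and with her agreement, AE and SAE collection continues through removal of the Sensor in place and a follow-up contact after it, and until the pregnancy outcome is known. State there how a pregnancy is recorded, and that outcomes go to the CEC and the DSMB. Add to the SAP a listing of pregnancies with outcome known or unknown, so that an absence of events can be read against the follow-up achieved.

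The clinical rule on discontinuation stays with the sponsor and needs no change for this purpose. The cost is some protocol, SAP and consent wording, a short outcome form if none exists, and a few contacts beyond nominal exit for a small number of subjects. Some may decline further contact; their outcomes should be shown as unknown.
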